5.0 Study Procedures

5.1 Study Design

5.1a. Design and specific aims: This is a phase 2, double-blind, multi-center RCT to compare the daily administration of 1200 mg oral LA to a placebo, as a disease-modifying treatment in PMS. A total of 118 subjects with PMS will be randomized 1:1 to LA or placebo. None of the study procedures involve usual care. All study procedures will be covered by study funding.

5.1b. Study population: A convenience sample of adults with PMS will be recruited from the study sites. The multi-site design of the trial is intended to promote generalizability of the study results.

5.1c. Study timeline and visit scheduling. The anticipated study recruitment period is for the first 18 months once the study is approved at the first study site or until enrolment is completed, whichever occurs first. The study will end when the last participant exits the study. There should be no more than 60 days inclusive between the screen and baseline visits. Subsequent study visits will occur at 3 months, 6 months, and every 6 months thereafter, each visit within +/- 2 weeks from the ideal visit based on the baseline/month zero (M0) visit. The MRI can take place up to 2 weeks prior to the baseline and final visits. Should the final MRI be postponed for any reason until after the

final visit, the subjects should continue taking study drug until the MRI has been done. Reasons for conducting visits outside the scheduling window are recorded.

Performance on clinical measures may be subject to variation due to the day-to-day fluctuations characteristic of PMS. Effects of fluctuations on study outcomes will be minimized by encouraging subjects to maintain their usual sleep, eating, and medication intake patterns on study days. Study visits will be scheduled at the same time-period each visit (morning versus afternoon). Study visits may be postponed for concurrent non-MS related illness affecting neurological performance on the discretion of the treating neurologist.

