Abnormal laboratory tests may be repeated immediately if laboratory testing error is suspected. Laboratory tests should be repeated within 1 month for any liver values reaching a Grade 2 or greater.

If laboratory liver value(s) are still Grade 2 or greater by 1 month, the investigational drug will be reduced by 50% and levels checked again within 1 month. The rationale is that liver-related abnormalities are often dose-dependent. If laboratory liver value(s) improve to Grade 1 or less, the study drug dose is then increased to the full dose. If the same subsequent laboratory value(s) worsen again at the full dose, the subject may continue for the study duration at the 50% dose as long as subsequent laboratory values do not meet Grade 2 or greater levels. If subjects on a 50% dose demonstrate continued Grade 2 value(s) at a maximum of 1 month, subjects should stop the investigational drug. Those subjects for whom laboratory values do not improve to Grade 1 or better levels after 2 months off study drug permanently stop study drug. Only two investigational drug cessations are allowed for each subject. Any subject who experiences a third Grade 2 or higher laboratory test must permanently discontinue the investigational drug. If in question, permanent study drug discontinuations can be discussed with the Medical Monitor to establish the relationship of the laboratory result to the investigational drug. Subjects continue study procedures following the study flowsheet until study end during any investigational drug dose reductions and temporary cessations (see 5.1d for special handling of MS clinical relapse evaluations).

Safety laboratory results will be reviewed by site treating neurologists within 3 business days to determine if dose adjustments or safety reporting is required along with documentation and reporting as required (section 6.0 Reporting).

Sexually active female subjects capable of becoming pregnant and female partners of sexually active male subjects will be asked to use effective birth control during the study. If a female participant or partner of a male participant becomes pregnant during the research study, study personnel must be notified immediately. Subjects will be advised not to breastfeed while taking this investigational drug. Screening for pregnancy in female subjects of child-bearing potential will be conducted via pregnancy tests at study visits.

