5.5b. Consent, medical history, general medical exam: The ICF will be presented by the PI, LSI, or designated study staff. After consent has been obtained, the rest of the study procedures can occur. The medical history and general medical exam is conducted by the treating neurologist for the purpose of eligibility.

5.5c. Vital signs: Resting blood pressure, pulse, and weight are collected by trained study staff at every study visit for the purpose of initial eligibility and ongoing health monitoring. Consistent methods of obtaining data (e.g. same resting period prior to blood pressure and pulse assessments, etc.) is encouraged across study visits. Height is assessed at the screening visit only.

5.5d. Concomitant medication review: Current use of prescribed scheduled and as needed medications as well as over the counter medications and supplements is recorded by the study staff and reviewed at the screen visit by the treating neurologist for study eligibility. Concomitant medications are reviewed at each subsequent visit by study staff and changes reviewed by the treating neurologist. Any start, stop, or change to MS disease-modifying therapies will be noted and dated for data analysis purposes. Supplements will be reviewed by research staff in case they contain lipoic acid or other potential confounders to the study results.

5.5e. Safety laboratory analyses: Laboratory studies will be collected from all subjects at the screening visit if not available within the prior 3 months for establishing eligibility. Additional laboratory analyses occur at visits M3, M6, M12, M18 and M24 to monitor blood cell count, renal function, liver function, urine protein, non-fasting blood glucose levels, HbA1c, and (for women of child-bearing potential) pregnancy testing. Subjects must have urine protein monitored every 3 months for the duration of the study. Pregnancy testing is additionally conducted at the baseline visit for women of child-bearing potential. This involves taking approximately 15-25 mL (3 to 5 teaspoons) of blood at each draw for a total of 90-150mL (2/3 cup) over the course of the study. Laboratory draws will be performed by trained phlebotomists using universal precautions.

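### Section 5.1m c gives no liver retest time after the return to full dose or after a restart, and its third-Grade-2 rule conflicts with its rule for continuing at half dose

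*Combined protocol and SAP*

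**What the plan says.** Section 5.1m c sets out a sequence for abnormal liver values. For a first abnormal result: "Laboratory tests should be repeated within 1 month for any liver values reaching a Grade 2 or greater". If the value is still Grade 2 or greater, "the investigational drug will be reduced by 50% and levels checked again within 1 month". The reason given is: "The rationale is that liver-related abnormalities are often dose-dependent". Then comes the return to full dose: "If laboratory liver value(s) improve to Grade 1 or less, the study drug dose is then increased to the full dose". The next sentence deals with a subject whose values get worse at full dose a second time: "the subject may continue for the study duration at the 50% dose as long as subsequent laboratory values do not meet Grade 2 or greater".

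The same paragraph allows two drug cessations per subject, requires permanent discontinuation at a third Grade 2 or higher test, and keeps subjects on the ordinary flowsheet during dose reductions and temporary cessations.

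The routine schedule is in section 5.5e: "Additional laboratory analyses occur at visits M3, M6, M12, M18 and M24 to monitor blood cell count, renal function, liver function". Footnote h of the flowsheet (5.5a) adds tests at M9, M15 and M21, but for urine protein only. Section 5.1d says that asymptomatic laboratory changes considered drug-related need no unscheduled visit and refers the reader to 5.1m.

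**The concern.** A subject who reaches the return to full dose has had a Grade 2 or greater value at that dose, had it confirmed on repeat, and then improved at half dose. On the paragraph's own dose-dependence reasoning, raising the dose is a foreseeable point for recurrence. Yet no retest is timed there, although the two preceding steps each have one. The 1-month repeat rule does not fill the gap, because it starts only once a new Grade 2 value is in hand.

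The later rules (continue at half dose, or stop) act on a result obtained at full dose. If that result comes only from the next routine panel, the time to detect a silent recurrence depends on which visit caught the first abnormality. Restart after a temporary cessation is less defined still: the two-cessation limit implies it, but the paragraph gives neither a restart dose nor a retest time.

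**Working it through.** The plan states no figure for this gap, so the check is interval arithmetic on its own schedule.

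**Inputs**
- Liver panels after baseline: M3, M6, M12, M18, M24 (5.5e).
- M9, M15, M21: urine protein only (5.5a, footnote h).
- t1, time to the confirmatory repeat: at most 1 month (5.1m c).
- t2, time on half dose to the recheck: at most 1 month (5.1m c).
- Visit window (5.1c): "Subsequent study visits will occur at 3 months, 6 months, and every 6 months thereafter, each visit within +/- 2 weeks".

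**Formula.** Let D be the months between the detecting panel and the next one. Time at full dose before the next required panel is D − (t1 + t2). With both retests at their latest, t1 + t2 = 2. With both done very quickly, the gap approaches D.

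Two weeks is 14/30.4375 = 0.46 month. Windows on both visits therefore move either end by up to 2 × 0.46 = 0.92 month.

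| Found at | Next panel | D | Gap on target dates (months) | Gap with windows (months) |
|---|---|---|---|---|
| M3 | M6 | 3 | 3 − 2 = 1, to under 3 | 1 − 0.92 = 0.1, to 3 + 0.92 = 3.9 |
| M6 | M12 | 6 | 6 − 2 = 4, to under 6 | 4 − 0.92 = 3.1, to 6 + 0.92 = 6.9 |
| M12 | M18 | 6 | 4 to under 6 | 3.1 to 6.9 |
| M18 | M24 | 6 | 4 to under 6 | 3.1 to 6.9 |

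On target dates, three of the four detecting visits that have a later panel give a gap of 4 months or more. For M18 the next panel is the final visit.

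**Which steps in 5.1m c carry a time**
- First Grade 2 or greater value: repeat within 1 month.
- First 50% reduction: recheck within 1 month.
- Continued Grade 2 at half dose: limited to 1 month, then stop.
- Return to full dose: none.
- Long-term half dose: later values are presupposed, with no interval.
- Off drug: judged after 2 months.
- Restart after a cessation: none.

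**The count of Grade 2 tests**
1. First Grade 2 value: test one.
2. Repeat still Grade 2, which triggers the reduction: test two.
3. Improvement at half dose, return to full dose, then Grade 2 again: test three.

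At the third step one sentence requires permanent discontinuation, while another allows the subject to continue at half dose. The two agree only if the count runs over episodes rather than tests, or if worsening at full dose means something short of Grade 2. The paragraph says neither.

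**The case against.** The strongest reply is that the plan does provide a later liver result. Subjects stay on the flowsheet, so a panel always follows, and a new Grade 2 value there starts the 1-month repeat again. The dose-dependence sentence explains the reduction and makes no promise about retesting after an increase. Other safeguards exist:
- telephone contacts about halfway between visits
- laboratory tests at the treating neurologist's discretion at unscheduled visits
- review of results within 3 business days
- reporting of every ALT or AST grade increase (6.3a)
- quarterly safety reports to the DSMB (6.8)

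Operating procedures that are not part of these documents may add detail.

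Much of this stands, and it rules out three stronger readings. A reader might infer that return to full dose is the only step without a 1-month check; the list of steps above shows that it is not. A reader might infer that nobody is scheduled to obtain the result at full dose; the next flowsheet panel does obtain it, only later. A reader might infer a strict contradiction with the rationale; it is an omission that sits badly with that rationale.

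The reply does not close the gap. A telephone call cannot detect a silent enzyme rise, a discretionary test is not a required one, and the review and reporting rules act only on results already obtained.

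**Conclusion.** The point holds in this form. Following 5.1m c and the flowsheet exactly, a subject with confirmed Grade 2 or greater values can be returned to full dose and remain untested for liver function for 4 to under 6 months on target dates, if first detected at M6, M12 or M18. Visit windows widen this to about 3.1 to 6.9 months, so 4 months is not a firm minimum. After detection at M3 the gap is 1 to under 3 months (about 0.1 to 3.9 with windows).

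These figures assume that the first abnormality is found at a scheduled panel, that each retest is done within its 1-month limit, and that no discretionary test is added. The documents do not say how often Grade 2 values are expected or when, so neither the number of subjects affected nor a typical gap can be given.

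The conflict between the third-Grade-2 rule and the rule for continuing at half dose is real when tests are counted literally. Together these make a safety weakness in a stated rule, which should be corrected.

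**What to change.** The sponsor and Medical Monitor should amend 5.1m c in three respects:
- Reconcile the dose-increase and restart steps with the timed checks in the same paragraph and with the flowsheet, and state when liver values are retested after each.
- State how a restart after a temporary cessation is handled, since the two-cessation limit presupposes one.
- Reconcile the third-Grade-2 rule with the rule for continuing at half dose, including what is counted (tests or episodes) and what worsening at full dose means.

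No retest interval, dose or re-escalation rule is proposed here; those are for the sponsor and Medical Monitor to decide.

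The cost is a few sentences of protocol text and a few extra blood draws, only in subjects who are re-escalated or restarted. Section 5.2h already provides compensation for extra laboratory visits.

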5.2 Recruitment Methods

5.2a. Recruitment goal: A total of 118 subjects will be recruited for the study which includes an expected 25% will-drop rate out after enrolment. More potential subjects will be screened than enrolled as it is expected that some will not meet eligibility requirements despite screening methods. The PM and DCC will monitor recruitment across study sites and provide feedback on when enrolment is complete in order to stop recruitment (see Communication Plan 8.0). Recruitment data and reasons for failing to enroll in the study will be collected periodically from all study sites for the purpose of encouraging enrolment and identifying barriers to participation.

5.2b. Subject Identification/Recruitment: Potential subjects for the study will be recruited by the site study staff from MS clinics and from the general public by methods approved by the study site's local Institutional Review Board (IRB) and/or a Central IRB. Sample advertisements recruitment flyers (Appendix B), recruitment letters to local MS practitioners (Appendix C), and telephone scripts for interested Veterans and nonveterans (Appendix D) are provided to each site. Email blasts to potential subjects will be sent from the National MS Society using the approved language contained in the recruitment flyers and letters (Appendix E). The NMSS promotes the study by hosting a webpage including a study summary, site locations, and study coordinator contact information. A short URL (Appendix X), linking to the NMSS webpage, may be distributed during media interviews, and added to promotion materials (Appendix Y) during MS related events, such as but not limited to, MS Walks, MS races, and MS support groups. ResearchMatch.org will be used as one of the recruitment tools for this research study/protocol. ResearchMatch Volunteers will be contacted through ResearchMatch.org using the approved language contained in the recruitment message (Appendix W). A release of information will be obtained as needed to request medical records for eligibility review prior to scheduling screening visits. Participants enrolled in the North American Research Committee on Multiple Sclerosis (NARCOMS) registry for Multiple Sclerosis will receive an approved study flyer in the mail. As with other recruitment tools, a release of information will be obtained as needed to request medical records for eligibility review prior to scheduling screening visits. We will make use of the contact information in [name] MS Research Repository (IRB#18541). This repository contains names and contact information of people interested in research participation. All subjects included in the repository have consented to being contacted for opportunities for participation in research. Initial contact with potential participants will be made by the research coordinator. The CCC will also work with the Recruitment Innovation Center (RIC) at Vanderbilt University to implement a 4-week, multicity, social media ad campaign in partnership with a marketing agency, Red Deluxe. Red Deluxe, a recruitment tool, will have 3rd party administrative access to a study Facebook page, managed by the CCC, in order to monitor and push Facebook ads to a targeted audience based on eligibility criteria and interest in MS. Examples and text of the components within the social media ad campaign include the Facebook page (Appendix Z), the Facebook Ads (Appendix AA), and the study webpage (Appendix BB) and content (Appendix CC), adhering to the VA Graphic Standards Guide.

5.2c. Recruitment of specific subpopulations. MS has a predilection for affecting women in a 3-4:1 ratio. Therefore we expect women to be adequately represented in this current study using a convenience sample. Minorities will not be preferentially recruited as there is no data to suggest a differential effect of LA on specific minority populations and/or with particular genetic characteristics. MS is rare in children, and progressive forms of MS rare within this small population. Therefore no children will be enrolled.

5.2d. Recruitment of Veterans: The pilot trial of LA recruited 21 Veterans from the total 51 subjects. The current proposed study has more restrictive inclusion criteria than the pilot study, requiring that subjects are ambulatory. Recruitment of non-Veterans and use of VA and non-VA study sites is necessary to fulfil the enrolment timeline.

5.2e. Sources of materials: Sources from human subjects will include blood and urine samples and data in the form of clinical tests (e.g. gait, neurologic exam), patient-reported outcomes, and radiographic information (MRI). Medical records will be reviewed prior to the screening visit to assess for eligibility and confirm MS diagnosis. Data will be collected solely for research purposes.

5.2f. Benefits: Subjects may or may not benefit directly from the study. The benefits to society may be the discovery of a safe and low-cost oral therapy to treat PMS.

5.2g. Costs to subjects: There will be no cost to subjects to participate in this study. The study drug and investigations will be covered by the study budget.

5.2h. Subject compensation: Subjects will receive \$50 per visit including unscheduled visits and \$25 for extra laboratory visits if needed and cannot be performed locally. In addition, subjects are compensated for travel with \$0.50/mile over 30 miles up to a maximum of \$100 per visit. The payments will be in the form approved by each local study site, and will cover the costs of transportation and meals during the study visits. The compensation is included in the ICF. Subjects will be provided compensation after each visit regardless if all procedures are completed.

5.3 Informed Consent Procedures

Subjects will be required to sign IRB- approved ICFs in accordance with FDA Code of Federal Regulations (21 CFR 50). The ICF will be presented to all potential subjects at the screening visit by study personnel who are trained in human subjects protection as required by the site IRBs. Briefly, the ICF describes the purpose of the study, procedures and participant involvement, potential risks, protection against risks, alternatives to participation, costs and compensation, confidentiality, right to withdraw, potential benefits, relevant contact personnel, and new information regarding the Health Insurance Portability and Accountability Act of 1996. Potential subjects will have ample time to read and ask questions, and, when satisfied, will document their consent to participate by signing the ICF. A copy of the ICF is given to the participant and the other retained for study records. All subjects must be able to provide informed consent in English. Potential subjects with impaired decision making ability will not be included in the study as they may not be able to adhere to study procedures per the eligibility requirements.

5.4 Inclusion/Exclusion Criteria

Inclusion criteria:

- i. Age > 18 years.
- ii. Previous diagnosis of RRMS or PPMS by 2010 revised McDonald criteria.(20)
- iii. Current SPMS or PPMS.
- iv. Progression of MS in the previous 2 years defined by medical record or reliable historical interview as:
 - a. Non relapse-related MS decline resulting in a 0.5 step change in EDSS, decline in T25FW, or other clinically documented decline (can be assigned retrospectively) if not on a DMT, OR
 - b. If currently on a DMT, non-relapse-related MS decline resulting in a 0.5 step change in EDSS, decline in T25FW, or other clinically documented decline (can be assigned retrospectively) while on the current DMT taken continuously for at least 1 year prior to enrolment.

- v. Able to give informed consent and to adhere to study procedures.
- vi. EDSS 3.0 to 6.5.

Exclusion criteria:

- A self-reported medical or neurological problem other than MS that is a cause of progressive or fluctuating gait dysfunction (e.g. worsening neuropathy, uncontrolled lower extremity arthritis, uncontrolled cardiopulmonary disease).
 Fixed and/or stable conditions of greater than 1 year that affect their gait are permitted (e.g. joint replacement, stable lumbar stenosis, remote alcoholism, remote stroke, etc.).
- ii. MRI constraints (metal implants including pacemaker, devices with electrodes, or shrapnel, excessive weight per site MRI requirements, need for sedation with non-oral agents due to claustrophobia or muscle spasticity).
- iii. MS clinical relapse in the 1 year prior to enrolment.
- iv. Unable to follow directions in English as standardized scales are not all validated in other languages.
- v. Current major disease or disorder other than MS (e.g., cancer, renal disease, end-stage cardiopulmonary disease, post-traumatic stress disorder, etc.) that may interfere with study procedures. Stable abnormal laboratory values of no more than Grade 1 determined to not be of clinical significance to the primary treating physician for that condition may be permitted per LSI discretion and comply with specific renal and liver testing requirements described in section 5.1m.
- vi. Pregnant or breast-feeding.
- vii. Insulin-dependent diabetes or diabetes not controlled on oral diabetes medications.
- viii. Scheduled (every 3 months or more frequently) IV or oral steroids in the year prior to enrolment.
- ix. IV or oral steroids in the 60 days prior to enrolment.
- x. Use of LA in the prior 2 years exceeding the equivalent of 1200mg daily for 3 months.
- xi. Participation in the pilot LA in SPMS trial.

